9.2. Definition of Serious Adverse Event

If an event is not an AE per definition above, then it cannot be an SAE even if serious conditions are met (eg, hospitalization for signs/symptoms of the disease under study, death due to progression of disease).

A Serious Adverse Event is defined as any untoward medical occurrence that, at any dose:

• Results in death

• Is life-threatening The term 'life-threatening' in the definition of 'serious' refers to an adverse drug experience that places the participant, in the opinion of the initial reporter, at immediate risk of death from the adverse experience as it occurred. This does not include an adverse drug experience that, had it occurred in a more severe form, might have caused death.

• Requires inpatient hospitalization or prolongation of existing hospitalization In general, hospitalization signifies that the participant has been detained (usually involving at least an overnight stay) at the hospital or emergency ward for observation and/or treatment that would not have been appropriate in the physician's office or outpatient setting. Complications that occur during hospitalization are AEs. If a complication prolongs hospitalization or fulfills any other serious criteria, the event is serious. When in doubt as to whether "hospitalization" occurred or was necessary, the AE should be considered serious. Hospitalization for elective treatment of a pre-existing condition that did not worsen from baseline is not considered an AE.

• Results in persistent or significant disability/incapacity

The term disability means a substantial disruption of a person's ability to conduct normal life functions.This definition is not intended to include experiences of relatively minor medical significance, such as uncomplicated headache, nausea, vomiting, diarrhea, influenza, and accidental trauma (eg, sprained ankle), that may interfere with or prevent everyday life functions but do not constitute a substantial disruption.

• Is a congenital anomaly/birth defect

• Other situations (Important Medical Event) An event that may not result in death, be immediately life-threatening, or require hospitalization, but may be considered serious when, based on appropriate medical judgment, the event may jeopardize the participant and may require medical or surgical intervention to prevent one of the outcomes listed in the above definition. Examples of such events include invasive or malignant cancers (excluding the disease[s] under study in oncology protocols), intensive treatment in an emergency department or at home for allergic bronchospasm, blood dyscrasias, or convulsions that do not result in hospitalization, or development of drug dependency or drug abuse.

9.3. Recording and Follow-Up of Adverse Events and/or Serious Adverse Events

Adverse Event and Serious Adverse Event Recording

- An AE/SAE that begins or worsens after informed consent is signed should be recorded on the Adverse Event Form in the eCRF. Conditions that were present at the time informed consent was given should be recorded on the Medical History Form in the eCRF.
- When an AE/SAE occurs, it is the responsibility of the investigator to review all documentation (eg, hospital progress notes, laboratory reports, and diagnostics reports) related to the event.
- The investigator (or delegate) will then record all relevant AE/SAE information in the eCRF.
- It is **not** acceptable for the investigator to send photocopies of the participant's medical records in lieu of completing the AE eCRF page.
- There may be instances when copies of medical records for certain cases are requested. In this case, all participant identifiers, with the exception of the participant number, will be redacted on the copies of the medical records before submission.
- The investigator will attempt to establish a diagnosis of the event based on signs, symptoms, and/or other clinical information. Whenever possible, the diagnosis (not the individual signs/symptoms) will be documented as the AE/SAE. When a clear diagnosis cannot be identified, each sign or symptom should be reported as a separate AE/SAE.

To the extent possible, each AE/SAE should be evaluated to determine:

- The severity grade (CTCAE Grade 1 to 5). See below for further instructions on the assessment of intensity.
- Whether there is at least a reasonable possibility that the AE is related to the study treatment (including itacitinib): suspected (yes) or not suspected (no). See below for further instructions on the assessment of causality.
- The start and end dates, unless unresolved at final follow-up.
- The action taken with regard to study drug as a result of the AE/SAE(s).
- The event outcome (eg, not recovered/not resolved, recovered/resolved, recovering/resolving, recovered/resolved with sequelae, fatal, unknown).
- The seriousness, as per the SAE definition provided in Section 9.2.
- The action taken with regard to the event. Note: If an AE is treated with a concomitant medication or nondrug therapy, this action should be recorded on Adverse Event Form and the treatment should be specified on the appropriate eCRF (eg, Prior/Concomitant Medications, Procedures and Non-Drug Therapy).

Assessment of Intensity

The severity of AEs will be assessed using CTCAE v5.0 Grades 1 through 5. If an event is not classified by CTCAE, the severity of the AE will be graded according to the scale below to estimate the grade of severity:

The investigator will make an assessment of intensity for each AE and SAE reported during the study and assign it to 1 of the following categories:

- **Grade 1:** Mild; asymptomatic or mild symptoms; clinical or diagnostic observations only; treatment not indicated.
- **Grade 2:** Moderate; minimal, local, or noninvasive treatment indicated; limiting age appropriate activities of daily living.

- **Grade 3:** Severe or medically significant but not immediately life-threatening; hospitalization or prolongation of hospitalization indicated; disabling; limiting self-care activities of daily living.
- **Grade 4:** Life-threatening consequences; urgent treatment indicated.
- **Grade 5:** Fatal.

Assessment of Causality

- The investigator is obligated to assess the relationship between study treatment and each occurrence of each AE/SAE. If reference therapy is used in combination with an Incyte study drug or multiple Incyte study drugs are used, the relationship to each study drug must be assessed (ie, for the Incyte product[s] and for the other product[s] that is used in combination with the Incyte product). If appropriate, the relationship to the combination may be assessed as well.
- A "reasonable possibility" of a relationship conveys that there are facts, evidence, and/or arguments to suggest a causal relationship, rather than that a relationship cannot be ruled out.
- The investigator will use clinical judgment to determine the relationship.
- The investigator will also consult the Reference Safety Information in the IB and/or Product Information, for marketed products, in his/her assessment.
- Alternative causes, such as underlying disease(s), concomitant therapy, and other risk factors, as well as the temporal relationship of the event to study treatment administration, will be considered and investigated.
- For each AE/SAE, the investigator **must** document in the medical notes that he/she has reviewed the AE/SAE and has provided an assessment of causality.
- With regard to assessing causality of SAEs:
 - There may be situations in which an SAE has occurred and the investigator has minimal information to include in the initial report. However, the causality assessment is one of the criteria used when determining regulatory reporting requirements. **Therefore, it is very important that the investigator always make an assessment of causality for every event before the initial transmission of the SAE.**
 - The investigator may change his/her opinion of causality in light of follow-up information and send a follow-up SAE report with the updated causality assessment.

Follow-Up of Adverse Events and Serious Adverse Events

- The investigator is obligated to perform or arrange for the conduct of supplemental measurements and/or evaluations as medically indicated or as requested by the sponsor to elucidate the nature and/or causality of the AE or SAE as fully as possible. This may include additional laboratory tests or investigations, histopathological examinations, or consultation with other health care professionals.
- New or updated information will be recorded in the originally completed eCRF.
- Any updated SAE data will be submitted to the sponsor (or designee) within 24 hours of receipt of the information.
- Once an AE is detected, it should be followed until it has resolved or until it is judged to be permanent; assessment should be made at each visit (or more frequently if necessary) of any changes in severity, the suspected relationship to the study drug, the interventions required to treat the event, and the outcome.
- When the severity of an AE changes over time for a reporting period (eg, between visits), each change in severity will be reported as a separate AE until the event resolves.

9.4. Reporting of Serious Adverse Events

Regardless of suspected causality (eg, relationship to study drug or study procedures), all SAEs occurring after the participant has signed the ICF through 30 days after the last dose of study treatment must be reported to the sponsor (or designee) within **24 hours** of learning of its occurrence, unless otherwise specified by the Protocol. The investigator will submit any updated SAE data to the sponsor (or designee) within 24 hours of it being available.

Investigators are not obligated to actively seek AE or SAE information after conclusion of the study participation. However, if the investigator learns of any SAE, including a death, at any time after a participant has been discharged from the study, and he/she considers the event to be reasonably related to the study treatment or study participation, the investigator must notify the sponsor (or designee) within 24 hours of becoming aware of the event.

After the initial AE/SAE report, the investigator is required to proactively follow each participant at subsequent visits/contacts. All SAEs will be followed until resolution, stabilization, the event is otherwise explained, or the participant is lost to follow-up (as defined in Section [7.3](#)).

Prompt notification by the investigator to the sponsor of a SAE is essential so that legal obligations and ethical responsibilities towards the safety of participants and the safety of a study treatment under clinical investigation are met.

If the SAE is not documented in the [IB](#) for the study drug (new occurrence) and is thought to be related to the sponsor's study drug, the sponsor or its designee may urgently require further information from the investigator for reporting to health authorities. The sponsor or its designee may need to issue an Investigator Notification to inform all investigators involved in any study with the same drug that this SAE has been reported. Suspected unexpected serious adverse reactions will be collected and reported to the competent authorities and relevant ethics committees in accordance with Directive 2001/20/EC, or as per national regulatory requirements in participating countries.

The sponsor has a legal responsibility to notify both the local regulatory authority and other regulatory agencies about the safety of a study treatment under clinical investigation. The sponsor will comply with country-specific regulatory requirements relating to safety reporting to the regulatory authority, IRB/IEC, and investigators.

Investigator safety reports must be prepared for suspected unexpected adverse reactions according to local regulatory requirements and sponsor policy and forwarded to investigators as necessary.

An investigator who receives an investigator safety report describing a SAE or other specific safety information (eg, summary or listing of SAEs) from the sponsor will review and then file it along with the [IB](#) and will notify the IRB/IEC, if appropriate according to local requirements.

Serious Adverse Event Reporting

SAE reporting procedures will follow the guidelines below from study initiation until study principal investigators are notified otherwise; should the sponsor switch the SAE reporting system to solely via the eCRF, the guidelines entitled "SAE Reporting via the EDC system" should be followed.

- Information about all SAEs is collected and recorded on the Adverse Event Form in the eCRF.

- The investigator must also complete the Incyte Serious Adverse Event Report Form, in English. Refer to the Incyte Reference Guide for Completing the Serious Adverse Event Report Form.
- Facsimile or email transmission of the Serious Adverse Event Report Form is the preferred method to transmit this information to the PhV/designee. The contact information of the sponsor's study-specific representatives is listed in the Study Reference Manual provided to each site. The original copy of the Serious Adverse Event Report Form and the confirmation sheet must be kept at the study site.
- Follow-up information is recorded on an amended or new Serious Adverse Event Report Form, with an indication that it is follow-up to the previously reported SAE and the date of the original report. The follow-up report should include information that was not provided on the previous Serious Adverse Event Report Form, such as the outcome of the event (eg, resolved or ongoing), treatment provided, action taken with study drug because of the SAE (eg, dose reduced, interrupted, or discontinued), or participant disposition (eg, continued or withdrew from study participation). Each recurrence, complication, or progression of the original event should be reported as follow-up to that event, regardless of when it occurs.
- In rare circumstances and in the absence of facsimile or computer equipment, notification by telephone is acceptable with a copy of the Incyte Serious Adverse Event Report Form sent by overnight mail or courier service. Initial notification via telephone does not replace the need for the investigator to complete and sign the Serious Adverse Event Report Form within the designated reporting time frames.
- Contacts for SAE reporting can be found in the Study Procedures Manual.

SAE Reporting via the EDC system:

- Information about all SAEs is collected and recorded on the Adverse Event Form in the eCRF.
- The investigator must report within 24 hours of learning of its occurrence any SAEs via the EDC system (primary method) or by completing the Incyte Serious Adverse Event Report Form, in English (only if EDC system is not available).
- Follow-up information is also recorded in the eCRF and transmitted to Incyte PhV via the EDC system. The follow-up report should include information that was not provided previously, such as the outcome of the event (eg, resolved or ongoing), treatment provided, action taken with study drug because of the SAE (eg, dose reduced, interrupted, or discontinued), or participant disposition (eg, continued or withdrew from study participation). Each recurrence, complication, or progression of the original event should be reported as follow-up to that event, regardless of when it occurs.
- In circumstances where the EDC system would not work properly, initial and/or follow-up SAE information shall be documented on new or amended Serious Adverse Event Report Form. Refer to the Incyte Reference Guide for Completing the Serious Adverse Event Report Form.
- Email transmission (or facsimile) of the Serious Adverse Event Report Form is the preferred method to transmit this information to the PhV/designee. The contact information of the sponsor's study-specific representatives is listed in the Study Reference Manual provided to each site. The original copy of the Serious Adverse Event Report Form and the confirmation sheet must be kept at the study site.
- Contacts for SAE reporting can be found in the Study Procedures Manual.

9.5. Emergency Unblinding of Treatment Assignment

Not applicable.

9.6. Pregnancy

Pregnancy, in and of itself, is not regarded as an AE unless there is suspicion that study drug may have interfered with the effectiveness of a contraceptive medication or method. When a pregnancy has been confirmed in a participant during maternal or paternal exposure to study drug, the following procedures should be followed in order to ensure safety:

1. The study drug must be discontinued immediately (female participants only).
2. If the female participant is no longer pregnant and meets the treatment continuation criteria within 12 weeks of the scheduled start of a cycle, study treatment may be resumed after approval has been received from the sponsor medical monitor.
3. The investigator must complete and submit the Incyte Clinical Trial Pregnancy Form to the sponsor or its designee within **24 hours** of learning of the pregnancy.

Data on fetal outcome are collected for regulatory reporting and drug safety evaluation. Follow-up should be conducted for each pregnancy to determine outcome, including spontaneous or voluntary termination, details of the birth, and the presence or absence of any birth defects, congenital abnormalities, or maternal and/or newborn complications, by following until the first well-baby visit. Pregnancy should be recorded on a Clinical Trial Pregnancy Form and reported by the investigator to the sponsor or its designee. Pregnancy follow-up information should be recorded on the same form and should include an assessment of the possible causal relationship to the sponsor's study drug to any pregnancy outcome, as well as follow-up to the first well-baby visit or the duration specified in local regulations, whichever is later. Refer to the Incyte Reference Guide for Completing the Clinical Trial Pregnancy Form.

Any SAE occurring during pregnancy of a study participant must be recorded on the Serious Adverse Event Report Form and submitted to the sponsor or designee.

Abnormal pregnancy outcomes (eg, spontaneous abortion, fetal death, stillbirth, congenital anomalies, or ectopic pregnancy) are considered SAEs (if occurring in the study participant) and must be reported as described in Section 9.4. If an abnormal pregnancy outcome is reported in a study participant's partner, the event should be reported to the sponsor on the Clinical Trial Pregnancy Form.

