7. DISCONTINUATION OF STUDY TREATMENT AND PARTICIPANT DISCONTINUATION/WITHDRAWAL

7.1. Discontinuation of Study Treatment

7.1.1. Reasons for Discontinuation

Participants **must** be discontinued from study treatment for the following reasons:

- BOS progression, defined as a $\geq 10\%$ absolute decrease in FEV₁ from pretreatment baseline, observed in at least 2 consecutive spirometric assessments at least 3 weeks apart.

Note: If the investigator believes that the participant has met criteria for BOS progression due to another reason (eg, infection), then continuation of treatment may be permitted after discussion with the medical monitor.

- An unacceptable toxicity is observed. An unacceptable toxicity is defined as an AE that is related to study treatment that, in the judgment of the investigator or the sponsor's medical monitor, compromises the participant's ability to continue study-specific procedures or is considered to not be in the participant's best interest.
- The investigator determines that there has been a loss of clinical benefit in the absence of Protocol-defined BOS progression.
- Development of post-transplant lymphoproliferative disorder.
- Development of BK viremia.

- Consent is withdrawn.
Note: Consent withdrawn means that the participant has explicitly indicated that they do not want to be followed any longer; in this case, no further data, except data in public domain, may be solicited from or collected on the participant. Participants may choose to discontinue study treatment and remain in the study to be followed for progression and survival.
- Further participation would be injurious to the participant's health or well-being, in the investigator's medical judgment.
- The study is terminated by the sponsor.
- The study is terminated by the local health authority, IRB, or IEC.

A participant **may** be discontinued from study treatment as follows:

- If, during the course of the study, a participant is found not to have met eligibility criteria, the medical monitor, in collaboration with the investigator, will determine whether the participant should be withdrawn from study treatment.
- If a participant is noncompliant with study procedures or study drug/treatment administration in the investigator's opinion, the sponsor should be consulted for instruction on handling the participant.

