- If the participant becomes pregnant. If the female participant is no longer pregnant and meets the treatment continuation criteria within 12 weeks of the planned reinitiation of treatment, study treatment may be resumed after approval has been received from the medical monitor (see Section [9.6](#)).

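### Protocol Sections 7.1.1 and 9.6 give pregnancy different discontinuation status (permitted versus required) and anchor the same 12-week restart window differently

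*Protocol*

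**What the plan says.** Protocol Section 7.1.1 contains two lists. The first opens "Participants must be discontinued from study treatment for the following reasons". It covers BOS progression, unacceptable toxicity, loss of clinical benefit, two named post-transplant complications, withdrawn consent, a general item on harm to the participant, and study termination. Pregnancy is not named. The second opens "A participant may be discontinued from study treatment as follows", and its third item begins "If the participant becomes pregnant". That item allows treatment to resume, with medical monitor approval, if the participant is no longer pregnant and "meets the treatment continuation criteria within 12 weeks of the planned reinitiation of treatment". It ends by pointing to Section 9.6.

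Section 9.6 lists what follows a confirmed pregnancy. The first step is "The study drug must be discontinued immediately (female participants only". The second allows resumption on nearly the same terms as 7.1.1, except that the criteria must be met "within 12 weeks of the scheduled start of a cycle".

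All of this is current protocol text, not amendment history.

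**The concern.** The same event has two different obligations attached to it. Section 7.1.1 sets its two list headings apart with emphasis on *must* and *may*, so the placement of pregnancy reads as deliberate. The protocol also treats 7.1.1 as the governing text for stopping: Section 6.1 lets participants stay on itacitinib until withdrawal is judged necessary under 7.1.1, and Section 4.1 sends the reader to Section 7.1 for further discontinuation criteria. A site working from that section finds pregnancy among the optional reasons.

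What is at stake is exposure of a fetus after the pregnancy is known. A second issue is whether a site can work out when restart is still allowed, because neither version of the 12-week window gives a date that can be fixed in advance.

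**Working it through.** No sample size, error rate or event count is involved, so the check sets the two sections side by side.

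| Element | Section 7.1.1 | Section 9.6 |
|---|---|---|
| Force of the stop | Permissive: "A participant may be discontinued from study treatment as follows" | Mandatory and immediate |
| Restart conditions | No longer pregnant; continuation criteria met | Same |
| Approval | Medical monitor | Sponsor medical monitor (same in substance) |
| Window length | 12 weeks | 12 weeks |
| Window anchor | "within 12 weeks of the planned reinitiation of treatment" | "within 12 weeks of the scheduled start of a cycle" |

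**Step 1: stop or continue.** There are two possible actions after a confirmed pregnancy.
- Stop at once: permitted by 7.1.1 and required by 9.6. Both are satisfied.
- Continue: permitted by 7.1.1 read alone, forbidden by 9.6. One is breached.

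The conflict therefore runs in one direction only. The nearest entry on the mandatory list, harm to the participant's own health or well-being, depends on the investigator's judgment and does not name pregnancy, so it does not close the gap.

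**Step 2: the anchor in 7.1.1.** Let C be the date the continuation criteria are met and P the planned restart date. The condition is that C falls within 12 weeks of P. Nothing in the text fixes P beforehand. If P is chosen once C is known, it can be set close to C and the condition always holds. The window is circular and excludes nobody.

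**Step 3: the anchor in 9.6.** This needs a scheduled cycle start. Table 8 specifies daily administration until discontinuation, and Tables 2 and 3 schedule visits by week. No cycle is defined. Suppose, as an assumption the text does not make, that a site substitutes the four-weekly visits that run from Week 4. Since 4 weeks is shorter than 12, every date is within 12 weeks of some scheduled visit, and the window again excludes nobody. It would bind only if tied to one particular visit, and the protocol names none.

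**Step 4: what both share.** The treatment continuation criteria on which both restart rules rely are not defined in the available text. Section 7.1.2 calls for an end-of-treatment visit on permanent discontinuation, and neither pregnancy provision says whether a stop that may be reversed triggers it.

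**Step 5: whether it is still live.** Section 2.3 and the Amendment 5 summary say Phase 2 was dropped and enrolment closed, with ongoing participants continuing on itacitinib. Table 3 keeps urine pregnancy tests during treatment for women of childbearing potential, and Table 11 puts them at every 28 days. The protocol therefore still looks for pregnancies on treatment.

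**The case against.** The strongest reply is that the pregnancy item in 7.1.1 cites Section 9.6, so a site that follows the reference reaches the mandatory rule. That stands as a real mitigation. It does not remove the conflict, because the reader then holds two texts of different force with no statement of which prevails.

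A second reply is that the sections can be harmonised: 7.1.1 would concern permanent discontinuation, which is optional because restart is possible, and 9.6 the immediate stop. Speaking of resumption does presuppose a stop, so the reading is arguable. But the protocol never draws that distinction. Both sections use the word *discontinued*, and both attach a restart provision.

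Third, safeguards reduce the chance of the situation arising: inclusion criterion 8 requires negative serum tests and contraception, exclusion criterion 18 bars pregnant women, and testing continues on treatment. Exposure before confirmation occurs under either section, so only exposure after confirmation is at issue. This limits the size of the point and leaves the contradiction in place.

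A reader might infer that the two sections give opposite instructions. They do not: *may* does not forbid stopping. A reader might also infer that the restart rules conflict throughout. They agree on the 12 weeks, the approval step and the conditions, and differ only in the anchor.

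**Conclusion.** The inconsistency is confirmed in current text. Pregnancy is a permitted reason to stop in 7.1.1 and a required, immediate one in 9.6. The restart windows share a length and an approval step but have different anchors, and neither anchor is workable as written.

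The size is modest. The documents do not say how many women of childbearing potential remain on treatment; the number could be zero. The planned Phase 1 total of about 24, both sexes included, gives only the scale of the pool. It would be tempting to say that the flaw touches every woman of childbearing potential enrolled, with unplanned fetal exposure as the result. The documents do not support that: the current text can matter only for those still on treatment, and its consequence is possible *continued* exposure, and only if a site acts on 7.1.1 without following the reference to 9.6.

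The conclusion assumes that *may* and *must* carry their ordinary meanings and that no definition of a cycle exists elsewhere in the protocol. It concerns consistency of a participant-safety rule. No endpoint, analysis population, sample size or estimate is affected.

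**What to change.** The sponsor should make two wording changes in the protocol.

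1. Reconcile Section 7.1.1 with Section 9.6 so that pregnancy has a single discontinuation status, stated identically in both places or stated once and cited from the other.
2. Reconcile the two restart windows on one reference point that exists in this trial and can be dated without knowing the restart decision.

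While doing so, it would help to say what the treatment continuation criteria are and whether a stop for pregnancy triggers the end-of-treatment visit in Section 7.1.2.

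Which discontinuation rule and which anchor to adopt is a clinical decision for the sponsor; nothing here favours either. The cost is protocol wording, with no new data collection and no change to the SAP.
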